2 SCHEDULE OF STUDY ASSESSMENTS

	Screening Assessment (30 days prior to initiation)	Weekly	Every 28 days (Day 1 of each cycle)	Week 16 and treatment discontinuation	Follow up ¹¹
Medical History	x				
Prior MDSTreatment	x				
ECOG Performance Status	x	X ⁸	x		
Pregnancy test ¹	x ²		x ³	X	
Serum ferritin level	x			X	
Serum erythropoietin	x				
Thyroid function tests ⁴	x			X	
aaPT/PTT/INR	x				
Serum chemistry ⁵	x	X ⁸	x	X	
Hematology, peripheral blood smear and RBC transfusion history ⁶	x ⁷	x ⁸	x	X	x
Physical examination	x		x	x	x
ECG	x		x ¹²		
Review medication log			x		
Response				x	

assessment ⁹					
Bone marrow aspirate & biopsy ¹⁰	X			X	
Cheek swab and toe nail clipping	X				

1. Women of childbearing potential only. Serum or urine pregnancy testing for β-HCG with a sensitivity of at least 50 mIU/mL. For further requirements for pregnancy testing and birth control, please see Appendix 1.
					

2. Within 7 days prior to the first day of study therapy.
					

3. Every 4 weeks while on study drug.
					

4. TSH (thyroid-stimulating hormone), T3, and T4 levels. Repeat thyroid function tests every three months.
					

5. Includes sodium, potassium, chloride, CO₂, calcium, magnesium, phosphorus, blood urea nitrogen (BUN), creatinine, glucose, albumin, total protein, alkaline phosphatase, total bilirubin, aspartate transaminase (SGOT/AST) or glutamic pyruvic transaminase (SGPT/ALT), lactate dehydrogenase (LDH), and uric acid.
					

6. Red blood cell (RBC) count, reticulocyte count, hemoglobin, hematocrit, white blood cell (WBC) count and differential, absolute neutrophil count (ANC), and platelet count required for protocol therapy must be done < 24 hours prior to the treatment cycle. Pretreatment CBC with differential and LFT's should be done < 1 week before randomization.
					

7. If not obtained within 7 days of the first day of study therapy, repeat the CBC on Day 0 of study treatment prior to start of study therapy.
					

8. Perform weekly for 4 weeks, then every 2 weeks for 5 to 8 weeks and monthly thereafter. Weekly CBC should be done when titrating or starting eltrombopag dosing until a stable platelet count is achieved.
					

9. Hematologic, pathologic, and cytogenetic response will be assessed according to criteria outlined in Section 6.1.2.
					

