
10. Bone marrow aspirate and biopsy with cytogenetic analysis and iron stains will be performed pre-study, and after 16 weeks of study treatment, and at the time of final response analysis. Additional biological studies obtained with bone marrow aspiration
					

are summarized in Section 14.

11. Every 3 months if patient is < 2 years from study entry, every 6 months if patient is 2-5 years from study entry, every 12 months if patient is 5-10 years from study entry. No specific requirements if patient is more than 10 years from study entry.

12. Only for patients receiving 300 mg eltrombopag dose or higher, resting 12-lead ECG will be obtained pre-dose on Day 1. A post-dose ECG should be obtained at Tmax (3 hours); if assessment cannot be performed at 3 hours, record actual time ECG was performed within a 2-6 hour window post-dose. A pre- and post-dose ECG as described above is required Week 2, week 4, 8 and 16.

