6.1 Inclusion Criteria

Subjects must meet the following inclusion/exclusion criteria to be eligible for the study.

- 1 Age \geq 18 years.
2. Patient must have a documented diagnosis of MDS according to World Health Organization (WHO) criteria (see Appendix IV) or non-proliferative chronic myelomonocytic leukemia (CMML) (WBC \leq 12,000/uL).
3. Patients must have International Prognostic Scoring System (IPSS) categories of Low- or Intermediate-1-risk disease (see Appendix 4).
4. Patients must have symptomatic anemia untransfused with hemoglobin \leq 10.0g/dL within 8 weeks of registration or with RBC transfusion-dependence (i.e., \geq 2 units/month) confirmed for a minimum of 8 weeks before randomization. Or patients have platelet $<$ 50,000/uL with hemoglobin $>$ 10.0 g/dL.
5. Patients must have IPSS score determined by cytogenetic analysis prior to randomization. Patients with cytogenetic failure and \leq 10% marrow blasts will be eligible.
6. Patients must be off all disease modifying therapy for MDS for 28 days prior to initiation of study treatment. Patients may receive hydrocortisone prophylactically to prevent transfusion reactions.
7. Patients must not have documented iron deficiency. All patients must have documented marrow iron stores. If marrow iron stain is not available, the transferrin saturation must be \geq 20% or a serum ferritin \geq 100 ng/100 mL or soluble transferrin receptor $<$ 5mg/L.
8. Women must not be pregnant or breastfeeding. Females of childbearing potential should have 2 negative pregnancy tests (sensitivity of at least 50 mIU/mL). The

first test should be performed within 10-14 days, and the second test within 24 hours prior to prescribing lenalidomide.

9. Females of reproductive potential must adhere to the scheduled pregnancy testing as required in the Revlimid REMS® program. Able to take aspirin (81 or 325 mg) daily as prophylactic anticoagulation (patients intolerant to ASA may use warfarin or low molecular weight heparin).

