6.2 Exclusion Criteria

A subject will not be eligible for inclusion in this study if any of the following criteria apply:

1. Pre-existing cardiovascular disease (including congestive heart failure, New York Heart Association [NYHA] Grade III/IV), or arrhythmia known to increase the risk of thromboembolic events (e.g. atrial fibrillation), or subjects with a QTc >450 msec (Male) and QTc > 470 msec (Female). Patients with history of atrial fibrillations or arrhythmias may be considered if in normal sinus rhythm at the time of registration and if cardiac echocardiogram shows no evidence of any cardiac thrombus.
2. Patients determined to be at increased risk of arterial or venous thrombosis by the investigator
3. Bone marrow fibrosis that leads to a dry tap.
4. Female subjects who are nursing or pregnant (positive serum or urine β -human chorionic gonadotropin (β -hCG) pregnancy test) at screening or pre-dose on Day 1.
5. Treatment with an investigational drug within 30 days or 5 half-lives (whichever is longer) preceding the first dose of study medication.
6. Patients with documented liver cirrhosis
7. Patients with known Splenic Vein Thrombosis.

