Mineral supplements (such as calcium, magnesium, aluminium, zinc, selenium or iron) are permitted during the study but study medication must be taken at least 4 hours before and 4 hours after consumption of these supplements. Similarly, eltrombopag must be taken at least 4 hours before and 4 hours after consumption of dairy products (such as milk, yogurt, and cheese).

HMG-CoA Reductase Inhibitors (statins)

Subjects will be permitted to use HMG-CoA reductase (3-hydroxy-3-methyl-glutaryl-CoA) inhibitors during the study, but these drugs should be used with caution and a 50% dose reduction of the HMG-CoA reductase inhibitor is recommended, with close monitoring for safety, such as liver chemistry and signs and symptoms of myolysis, and efficacy, such as cholesterol and triglycerides (refer to individual product information for monitoring recommendations).

Preclinical data showed that eltrombopag is an inhibitor of the transporters OATP1B1 and BCRP. Therefore, a clinical drug interaction study to evaluate the impact of eltrombopag on the PK of rosuvastatin, an OATP1B1 and BCRP substrate, was conducted in healthy subjects. Co-administration of eltrombopag 75 mg once daily for 5 days with a single 10mg dose of rosuvastatin administered on Day 5 increased plasma rosuvastatin C_{max} 2.03-fold and AUC(0-∞) 55%. Concomitant administration of eltrombopag and other OATP1B1 or BCRP substrates should be used with caution.

Concomitant MDS Therapy

G-CSF is allowed during the study for subjects with severe neutropenia and recurrent infections. Subjects who enter the study on G-CSF should continue at the same dose schedule until the optimal dose of study medication has been established.

Any change in dosage of any concomitant medication (change in dose or frequency) MUST be recorded in the eCRF, to include: drug name, dose, frequency of administration, start and stop dates and indication.

Prohibited Medications and Non-Drug Therapies

Subjects must abstain from using prohibited prescription or non-prescription drugs within 7 days or 5 half-lives (whichever is longer) prior to the first dose of study

medication until completion of follow-up procedures (Section 5.3, Exclusion Criteria).

The following medications are prohibited during the study:

- Any other TPO-R agonists

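### The ferritin floor in inclusion item 7 is printed per 100 mL, which is 1 ng/mL, so the fallback for patients without a marrow iron stain screens out almost no one

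*Combined protocol and SAP*

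**What the plan says.** Item 7 of section 6.1 has three parts.

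- It opens with two general requirements: "Patients must not have documented iron deficiency. All patients must have documented marrow iron stores".
- It then provides a substitute: "If marrow iron stain is not available, the transferrin saturation must be" at least 20%, or serum ferritin must be at least "100 ng/100 mL or soluble transferrin receptor" below 5 mg/L. The three markers are alternatives.

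Other sections bear on how often the substitute is used and what follows from it.

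- Section 2, footnote 10: "Bone marrow aspirate and biopsy with cytogenetic analysis and iron stains will be performed pre-study".
- Section 6.2, exclusion 3: "Bone marrow fibrosis that leads to a dry tap".
- Section 2, schedule: "Serum ferritin level" is listed at screening. Transferrin saturation and soluble transferrin receptor are not listed.
- Section 8.5: "Mineral supplements (such as calcium, magnesium, aluminium, zinc, selenium or iron) are permitted during the study", subject to spacing from eltrombopag.
- Section 14.2 names major erythroid response as the primary outcome. It judges a single response rate against 25%, continuing with 7 or more responders of 25 and declaring success with 17 or more of 52.

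**The concern.** A cut-off of 1 ng/mL does almost no screening. Because one satisfied marker is enough, an ineffective ferritin option also makes the other two options nearly irrelevant. Ferritin is also the marker most likely to be on hand when the stain is missing, since it is the only one of the three that the schedule requires.

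The item exists to keep iron deficiency out of a trial judged on red-cell response. Iron-deficient patients who take iron on study could show a hemoglobin rise unrelated to the study drugs. Those who do not take it could fail to respond for a reason unrelated to them. Every patient is assigned to protocol therapy and the comparison is with a fixed rate, so no untreated group would reveal either effect.

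**Working it through.** **Unit.** 100 ng / 100 mL = 1 ng/mL. If the denominator was meant to be 1 mL, the floor would be 100 ng/mL, a 100-fold difference. The documents give no derivation or source for the cut-off, so they cannot settle which was meant.

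**Logic of the fallback.** A patient without a stain passes if transferrin saturation ≥ 20%, or ferritin ≥ 1 ng/mL, or soluble transferrin receptor < 5 mg/L. The patient fails only if all three of these hold: saturation < 20%, ferritin < 1 ng/mL and receptor ≥ 5 mg/L. Whoever clears 1 ng/mL passes this sentence whatever the other two results are.

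**Who is exposed.** Set side by side, the passages narrow the group. The serum route opens only without a stain; a stain is scheduled before study; a dry tap from fibrosis is excluded; and documented iron deficiency is barred separately. What remains is patients with no usable stain whose deficiency has not been documented in some other way. The documents give no count.

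**Illustration of size.** Inputs from section 14.2: p0 = 25%, first stage 7 of 25, final 17 of 52. Assumptions, not in the documents: a share f = 2% of patients affected (0.02 × 52 = 1.04, about one patient), with response rate q among them. The overall rate is

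p = (1 − f) × 0.25 + f × q.

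The chance of declaring success is the exact two-stage sum over first-stage responders x:

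P(success) = Σ (x = 7 to 25) P(X1 = x) × P(X2 ≥ 17 − x), with X1 ~ Bin(25, p) and X2 ~ Bin(27, p).

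| Case | p | P(success) |
|---|---|---|
| None affected | 0.250 | 11.8% |
| 2% affected, none respond | 0.98 × 0.25 + 0.02 × 0 = 0.245 | 10.2% |
| 2% affected, half respond | 0.98 × 0.25 + 0.02 × 0.5 = 0.255 | 13.5% |
| 2% affected, all respond | 0.98 × 0.25 + 0.02 × 1 = 0.265 | 17.5% |

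The 11.8% baseline is above the 10% ceiling stated in section 14.2. That is a separate matter: requiring 8 or more of 25 to continue gives 9.9%, which agrees with the stated ceiling. Under that boundary the all-respond case is 14.8% and the none-respond case 8.6%, so the pattern is the same.

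**The case against.** The strongest case against is that this is a unit query and little more. Much of it stands.

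- A reader might infer that the ferritin line lets iron-deficient anemia into the trial generally. The documents do not support that. The line is reached only without a stain, and the plan schedules one for everyone before study.
- A reader might construct a patient with saturation 8%, raised transferrin receptor and ferritin 5 ng/mL, and say that this patient satisfies item 7. That patient does pass the fallback sentence. But the item's first sentence, "Patients must not have documented iron deficiency", is a separate requirement, and those results on file would arguably be documented deficiency.
- A reader might infer an inflated false-success rate. The 17.5% figure needs 2% affected and every one of them responding. The documents support neither input, and if none respond the error moves the other way.
- The route from deficiency to a counted response is long: no stain, undocumented deficiency, iron taken on study, and a response lasting more than 8 weeks. Section 8.5 permits mineral supplements while discussing spacing from eltrombopag; it does not describe iron treatment.
- Section 11 counts a hemoglobin rise of 1.5 g/dL as an erythroid response, but section 14.2 names major erythroid response. The only description of that term, for a prior study in section 3.4, is sustained transfusion independence or a rise above 2 g/dL. A gain of 1.5 g/dL may not meet it.

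What the objection does not remove is the threshold itself. The first sentence bars only deficiency that is documented. Without a stain, documentation depends on serum markers, and the one scheduled marker carries a floor that almost anyone clears. The dry-tap exclusion covers fibrosis only, and the protocol keeps the fallback for other reasons a stain may be missing. If a site did treat a low saturation as documented deficiency, item 7 would accept and reject the same patient, which is itself a reason to correct it.

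**Conclusion.** The point holds for the fallback group only. The printed ferritin floor is 1 ng/mL, and with the 'or' structure the fallback rejects almost no one. The conversion is certain. That almost no one is rejected rests on the assumption that usual ferritin values lie far above 1 ng/mL.

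The effect on the trial's conclusion is neither quantified nor given a direction by the documents. With about one affected patient in 52, the chance of success at a true 25% rate ranges from 10.2% to 17.5%, around 11.8%. It is small if the fallback is rarely used. The correction is worth making because the criterion cannot do its job as printed and the change costs almost nothing, not because a material bias has been shown.

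**What to change.** The sponsor should confirm the intended ferritin value and unit against its source, then correct the unit in item 7 and on the eligibility checklist. In the same edit, reconcile the fallback with the two sentences before it: state whether marrow iron stores are required of all patients or may be replaced by serum markers, and whether a patient who passes on one marker but has other results pointing to deficiency is barred by the first sentence.

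The cost is one unit and a clarifying sentence. Ferritin is already measured at screening, so correcting the unit needs no new test or visit and no change to the sample size. The downside is that a few patients without a stain may no longer qualify.

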6.2 Exclusion Criteria

A subject will not be eligible for inclusion in this study if any of the following criteria apply:

1. Pre-existing cardiovascular disease (including congestive heart failure, New York Heart Association [NYHA] Grade III/IV), or arrhythmia known to increase the risk of thromboembolic events (e.g. atrial fibrillation), or subjects with a QTc >450 msec (Male) and QTc > 470 msec (Female). Patients with history of atrial fibrillations or arrhythmias may be considered if in normal sinus rhythm at the time of registration and if cardiac echocardiogram shows no evidence of any cardiac thrombus.
2. Patients determined to be at increased risk of arterial or venous thrombosis by the investigator
3. Bone marrow fibrosis that leads to a dry tap.
4. Female subjects who are nursing or pregnant (positive serum or urine β -human chorionic gonadotropin (β -hCG) pregnancy test) at screening or pre-dose on Day 1.
5. Treatment with an investigational drug within 30 days or 5 half-lives (whichever is longer) preceding the first dose of study medication.
6. Patients with documented liver cirrhosis
7. Patients with known Splenic Vein Thrombosis.

6.3 Visit schedule and assessments

Screening Assessments and all on study scheduled visits and assessments are outlined in Section 2 Table of Study Assessments.

At treatment discontinuation, subjects will undergo off study evaluations per the Schedule of Assessments, Section 2. In addition, a safety assessment will be done approximately 28 days post the last dose of protocol therapy.

7 PATIENT REGISTRATION

Central registration for this study will take place at the Montefiore-Einstein Center Monday through Friday 9:00am – 5:00pm Eastern Standard Time. Eligibility Checklist with supporting documentation, On Study Form and the signed Patient Consent Form must be faxed to the clinical trials office at the Montefiore-Einstein Center, [contact], at the time of registration and prior to patient treatment.

At the time of registration, all eligibility criteria must be checked. Patients must meet all of the eligibility requirements listed in the Eligibility Checklist. Patients must not start protocol treatment prior to registration.

It is the treating physician's responsibility to review all data submitted to the Clinical Trials Office for accuracy and completeness and he/she must sign the off study form.

8 DRUG ADMINISTRATION

8.1.1 Dosing regimen

All toxicities should be graded according to the Common Terminology Criteria for Adverse Events (NCI CTC ver4.03). For patients who experience treatment delays due to toxicity, final response assessment will be delayed according to the number of 28 day cycles off of study treatment.

Subjects will be evaluated for adverse events (AEs) at each visit.

8.1.2 Dose Modifications

Dose Reductions for lenalidomide

Table 1 gives the dose levels for the dose reduction steps for adverse events.

Table 1: Dose Reduction Steps for lenalidomide

Starting dose 10 mg/day on days 1-21, followed by 7 days of no therapy

Dose level -1 5 mg daily

Dose level -2 5 mg every other day (qod)

Patients who experience limiting neutropenia after prolonged treatment with 5 mg every other day may resume treatment at the same dose upon hematologic recovery.

Dose Modifications for Neutropenia

Hold lenalidomide for a decline in neutrophil count to $< 500/\mu\text{L}$ that does not respond to myeloid growth factor administration. Lenalidomide should be resumed at the next dose

reduction step when neutrophil count is $> 500/\mu\text{L}$. **Dose Modifications for Thrombocytopenia**

For patients with a baseline platelet count $< 50,000/\mu\text{L}$;

Start eltrombopag when the platelet count is $< 50,000/\mu\text{L}$. Start Lenalidomide (AND STOP eltrombopag) only after platelet count $> 50,000$ (non transfused) for at least 2 weeks. If platelet fall $< 50,000/\mu\text{L}$ after resuming lenalidomide again then again hold dose and start Eltrombopag again. Once plt count $> 50,000$ for two weeks, then start lenalidomide and give eltrombopag concomitantly.

For patients with a baseline platelet count $\geq 50,000/\mu\text{L}$;

Start Lenalidomide alone. If plt count falls below $50,000/\text{L}$ then follow algorithm as above.

Patients who do not experience platelet recovery within 8 weeks of starting Eltrombopag should be removed from study and complete all off study evaluations.

Dose modifications for hemoglobin levels:

For those patients experiencing a rise in hemoglobin $> 14 \text{ g/dL}$, Lenalidomide should be withheld until the hemoglobin is $< 12 \text{ g/dL}$, at which time treatment can be resumed according to the dose adjustment recommendations in Table 1. For those patients previously adjusted to the lowest CC-5013 (lenalidomide) dose, the CC-5013 (lenalidomide) schedule should be changed to a 2 week treatment schedule every 4 weeks.

Dose Modifications for Other Adverse Events

Dose interruption and modification guidelines for other adverse events are in Table 2. Lenalidomide should be held for any $>$ grade 3 adverse events with suspected drug association until resolution to $<$ grade 2. For any patients who do not experience resolution to $<$ grade 2 within 4 weeks should be removed from study and complete all off-study evaluations. For patients with thromboembolic events, both agents should be discontinued and not resumed until resolution with proper prophylaxis according to the discretion of the treating investigator.

NOTE: Patients will be removed from study if lenalidomide is held for longer than 8 weeks for treatment-related toxicity.

Table 1: Dose Modifications for CC-5013 (lenalidomide)

System	NCI CTCAE Grade	Action
Coagulation	Venous thrombosis/embolism \geq Grade 3	
 Hold (interrupt) dose and start anticoagulation; resume CC-5013 (lenalidomide) at investigator's discretion (maintain dose level).
Skin	Desquamating rash (blistering)	
 Discontinue study treatment.
	Non-desquamating rash Grade 2	
 If Grade 2, interrupt CC-5013 (lenalidomide) therapy. Resume CC-5013 (lenalidomide) when the rash resolves to \leq Grade 1 (decrease one dose level).
	Grade \geq 3	
 Discontinue CC-5013 (lenalidomide) study drug.
Neurology	Neuropathy Grade 3	
 If Grade 3, interrupt CC-5013 (lenalidomide) 3 therapy. Resume CC-5013 (lenalidomide) when the neuropathy resolves to \leq Grade 1 (decrease one dose level).
	Grade 4	
 Discontinue CC-5013 (lenalidomide) study drug.

System	NCI CTCAE Grade	Action
Allergy	Allergic reaction Grade 2	
 If Grade 2, interrupt CC-5013 (lenalidomide) therapy. Resume CC-5013 (lenalidomide) when symptoms resolve to \leq Grade 1 (decrease one dose level).
	\geq Grade 3	
 Discontinue CC-5013 (lenalidomide) study drug.
Gastrointestinal	Constipation \geq Grade 3	
 Hold (interrupt) dose. Initiate bowel regimen, and resume CC-5013 (lenalidomide) when constipation resolves to \leq grade 2 (decrease one dose level).
Endocrine	Hyperthyroidism or hypothyroidism	
 Interrupt CC-5013 (lenalidomide) and initiate appropriate medical therapy. Resume CC-5013 (lenalidomide) at investigator's discretion (maintain dose level).
Cardiac Arrhythmias	Sinus bradycardia/other cardiac arrhythmia Grade 2	
 Hold (interrupt) dose. Follow at least weekly. If the toxicity resolves to \leq grade 1 resume at next lower dose level.
	\geq Grade 3	
 Discontinue CC-5013 (lenalidomide) study drug.
Other Toxicity	Other non-hematologic toxicity assessed as CC-5013 (lenalidomide)-related \geq Grade 3	
 Hold (interrupt) dose. Follow at least weekly. If the toxicity resolves to \leq grade 2 resume at next lower dose level.

[figure not shown]
Dosing for Eltrombopag

Patients will initially be started on 100 mg eltrombopag (50 mg for subjects of East Asian heritage). Thereafter, dependent on the platelet response (see Table 3 below), the dose of study medication can be increased every 2 weeks, up to a maximum dose of 300 mg/day (150 mg/day for subjects of East Asian heritage).

Modified dosing for subjects of East Asian heritage (i.e., Japanese, Chinese, Taiwanese and Korean) has been implemented for the following reasons. In healthy Japanese subjects, plasma eltrombopag AUC(0- τ) was approximately 80% higher when compared to non-Japanese healthy subjects who were predominantly Caucasian. Similarly, in patients with ITP, plasma eltrombopag exposure was approximately 70% higher in East Asian (i.e., Japanese, Chinese, Taiwanese and Korean) subjects as compared to non-East Asian subjects who were predominantly Caucasian.

Intra-individual dose adjustments will be made in a stepwise fashion, by sequentially increasing to dose levels of 100 mg, 200 mg or 300 mg as needed (50, 100, 150 mg for subjects of East Asian heritage). Titration of study medication with different dosages on different days will be permitted where needed in order to maintain a stable platelet count in the safe range without exceeding platelet counts >400 Gi/L. The dosing regimen of eltrombopag must be individualized based on platelet counts. Use the lowest effective dosing regimen to maintain platelet response.

Figure 4: Schema of dose adjustments for eltrombopag

Eltrombopag must be taken either in a fasted state (i.e., 1 hour before or 2 hours after food) or taken with food low in calcium (no dairy products). There must be at least a 4-hour interval between eltrombopag and other medications, food, or supplements containing polyvalent cations such as iron, calcium, aluminum, magnesium, selenium, and zinc, including dairy products. After any eltrombopag dose adjustment, monitor platelet counts at least weekly for 2-3 weeks.

At eltrombopag dose levels 200 mg and above, subjects who have discontinued other drugs known to prolong QT and who still have a QTc >480 msec will be excluded

Table 2: Guidelines for Eltrombopag Dose Adjustments

Platelet Counts	Dose Adjustments
No platelet response	
Increase daily dose to the next dose level
 
If platelet counts do not stabilize at desired levels, consider dosing regimens such as different dose levels on alternating days.
 
Wait for 2 weeks to see the effect of the dose increase on platelet response before another dose increase is considered.

200-400 k/uL	
If no post-baseline BM examination has been performed:
 
Decrease daily dose considering dosing regimens such as different dose levels on alternating days.
 
If platelet counts remain between 200-400 k/uL, wait for 2 weeks to see the effect of the dose decrease on platelet response before another dose decrease is considered.

	
If BM blasts have decreased:
 
Maintain dose level and monitor platelet counts weekly.

	
If BM blasts have increased:
 
Decrease daily dose considering dosing regimens such as different dose levels on alternating days.
 
If platelet counts remain between 200-400 k/uL, wait for 2 weeks to see the effect of the dose decrease on platelet response before another dose decrease is considered

>400k/uL	Interrupt treatment and monitor platelets twice a week until platelet counts fall below 150 k/uL and restart treatment by reducing the daily dose to the next dose level considering dosing regimens such as different dose levels on alternating days.
----------	---

During eltrombopag therapy, CBCs, including platelet count and peripheral blood smears, should be assessed weekly until a stable platelet count has been achieved. CBCs including platelet counts and peripheral blood smears, should be obtained monthly thereafter. Blasts will be monitored as indicated in flowchart:

Algorithm for Blast Count Monitoring

[figure not shown]

Figure 5: Schema for blast count monitoring

Special Handling Instructions

Females of childbearing potential should not handle or administer lenalidomide unless they are wearing gloves.

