develops new or worsening morphological abnormalities or cytopenia, treatment with eltrombopag should be discontinued and a bone marrow biopsy, including staining for fibrosis considered.

Recurrence of Thrombocytopenia After Cessation of Eltrombopag

Discontinuation of eltrombopag may result in recurrence of thrombocytopenia. This recurrence of thrombocytopenia may increase the patient's risk of bleeding, particularly if eltrombopag is discontinued while the patient is on anticoagulants or antiplatelet agents. In the 3 controlled ITP clinical studies, transient decreases in platelet counts to levels lower than baseline were observed following discontinuation of treatment in 8% and 8% of the eltrombopag and placebo groups, respectively. Serious hemorrhagic events requiring the use of supportive ITP medications occurred in 4 severely thrombocytopenic patients within one month following the discontinuation of eltrombopag; none were reported among patients in the placebo group.

Following discontinuation of eltrombopag, weekly CBCs, including platelet counts for at least 4 weeks should be obtained and alternative treatments for recurrence of thrombocytopenia, according to current treatment guidelines, considered.

Thrombotic/thromboembolic complications

Eltrombopag may increase the risk of thrombotic/thromboembolic events.. Excessive doses of eltrombopag may increase platelet counts to a level that produces thrombotic/thromboembolic complications.

In the 3 controlled ITP clinical studies, thrombotic/thromboembolic complications occurred in four patients in the groups that received eltrombopag and none in the placebo groups. Thrombotic/thromboembolic complications have also been reported in the ITP extension study. The thrombotic/thromboembolic complications in patients with chronic ITP included both venous and arterial events and were observed at low and normal platelet counts.

Use caution when administering eltrombopag to patients with known risk factors for thromboembolism (e.g., Factor V Leiden, ATIII deficiency, antiphospholipid syndrome, chronic liver disease). To minimize the risk for thrombotic/thromboembolic complications, do not use eltrombopag in an attempt to normalize platelet counts. Follow the dose adjustment guidelines to achieve and maintain a platelet count of $\geq 50 \times 10^9/L$ as necessary to decrease the risk for bleeding

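### Section 8.1.2: the Coagulation row of the lenalidomide table omits the paragraph's condition that a clot resolve before restart, and covers fewer events and only one of the two drugs

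*Combined protocol and SAP*

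**What the plan says.** Section 8.1.2, under other adverse events, first gives a paragraph of rules. Its rule after a thromboembolic event is that "both agents should be discontinued and not resumed until resolution with proper prophylaxis according to the discretion of the treating investigator". That sentence sets no grade limit and does not separate venous from arterial events.

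The lenalidomide dose-modification table follows. Its Coagulation row is headed "Venous thrombosis/embolism" and starts at Grade 3. The action begins "Hold (interrupt) dose and start anticoagulation; resume CC-5013 (lenalidomide" and goes on to leave restart to the investigator, at an unchanged dose level.

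No text says which instruction governs. The paragraph's own pointer does not help: it states that "Dose interruption and modification guidelines for other adverse events are in Table 2", but the table carrying that number is captioned "Table 2: Guidelines for Eltrombopag Dose Adjustments" and is keyed to platelet counts.

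**The concern.** Dose-modification tables are what sites tend to use when an event occurs. Here the row is looser than the paragraph it sits beneath. It drops the condition that the event resolve before restart, it covers only part of the range of events, and it stops one drug where the paragraph stops two.

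Both drugs carry the risk. Thrombosis is on the expected-event list for lenalidomide in Section 9.1. Section 9.2 reports thrombotic complications in four patients on eltrombopag and none on placebo in the three controlled ITP studies, and says that events in ITP patients "included both venous and arterial events". Under Section 5.1, a patient whose platelets fall a second time receives both drugs together for all later cycles, so a patient with a clot may be taking both. At stake is patient safety after a clot: an early restart of lenalidomide, or eltrombopag left running.

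**Working it through.** No arithmetic applies. The check sets the two instructions side by side and asks what a site would do under each.

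| Element | Paragraph | Coagulation row |
|---|---|---|
| Events covered | Any thromboembolic event | Venous, Grade 3 or higher |
| Drugs stopped | Lenalidomide and eltrombopag | Lenalidomide |
| Resolution before restart | Required | Not stated |
| Antithrombotic cover | Prophylaxis, as a condition of restart | Anticoagulation, at onset |
| Investigator discretion | Yes | Yes |
| Restart dose of lenalidomide | Not stated | Unchanged |

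**Step 1: venous event, Grade 3 or higher.** A site can stop both drugs, anticoagulate, wait for resolution, and then restart lenalidomide at the same dose at its discretion. That satisfies both texts. The reverse fails: a site following only the row may restart before resolution and is not told to stop eltrombopag.

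**Step 2: venous event below Grade 3.** The paragraph stops both drugs. The Coagulation row does not apply, and the Other Toxicity row also starts at Grade 3, so the table gives no action.

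**Step 3: arterial event.** The Coagulation row does not apply. If the event is Grade 3 or higher and judged related to lenalidomide, a site might use the Other Toxicity row, which holds lenalidomide and resumes it one level lower once the event is Grade 2 or less. Otherwise the table gives no action. In neither case does it stop eltrombopag.

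**Step 4: could a reader take the row's silence as intended?** Eight entries in the table allow restart. Six name the improvement needed first, and all six lower the dose: non-desquamating rash, neuropathy, allergic reaction, constipation, arrhythmia and other toxicity. The other two, Coagulation and Endocrine, name no improvement and keep the dose. Against that pattern, a table user could reasonably conclude that clot resolution is not required.

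**Step 5: does other text close the gap?**
- The general hold rule in the same paragraph is printed as applying above Grade 3 to events with suspected drug association. The inequality sign may have been damaged in PDF extraction. Even if Grade 3 is included, the rule covers lenalidomide only, and a table-only reader has already passed over that paragraph.
- The eltrombopag adjustment table has no thrombosis entry.
- The stopping list in Section 8.3 has a general clause for harmful adverse events but names no thrombotic event.
- Section 9.2 advises caution and dose adjustment but does not say to stop eltrombopag after a clot.

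The explicit instruction to stop eltrombopag after a clot therefore rests on the one sentence that the row does not repeat.

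**The case against.** The strongest reply is that there is no contradiction. The paragraph introduces the table, covers both drugs and all thromboembolic events, and can be obeyed together with the row. The row's silence on eltrombopag follows from its place in a lenalidomide table. Eltrombopag is often not being taken alongside lenalidomide, because it is stopped when lenalidomide first starts, and Section 14.2 assumes that 10-20% of patients with higher platelet counts may never need it. Exclusion 2 in Section 6.2 removes patients whom the investigator judges to be at increased risk of thrombosis.

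Most of this stands, and it limits the point to a site that works from the table alone. It does not remove the point: the row omits a safety condition that its companion text imposes, and nothing tells the site to read the two together.

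Three stronger readings are tempting, and the documents do not support them.
- A reader might infer that the paragraph demands resolution while the row rests on discretion alone. Discretion appears in both, and the row also requires anticoagulation.
- A reader might infer that the row creates a bleeding hazard, because Section 9.2 warns of bleeding "if eltrombopag is discontinued while the patient is on anticoagulants or antiplatelet agents". But the row does not stop eltrombopag; the paragraph does. The monitoring after stopping is already in Section 9.2: "weekly CBCs, including platelet counts for at least 4 weeks should be obtained".
- A reader might treat restart at the full dose as a discrepancy. The paragraph sets no restart dose, so there is nothing for the row to conflict with.

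**Conclusion.** The point holds in a narrow form. The Coagulation row omits the resolution condition and narrows the scope from any thromboembolic event and both drugs to venous events of Grade 3 or higher and lenalidomide. It matters where a site uses the table without the paragraph; how often that would happen cannot be judged from the documents.

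No numerical size is attached. The documents give no thrombosis rate for this population. An assumed rate would give the chance that a clot occurs, not the chance that a drug is restarted too early. A reader might also infer an effect on the trial's conclusions, but none is shown: Section 14.1 keeps every treated patient in the safety analyses, and the sample size, response count and error rates in Section 14.2 do not depend on this row. It is a modest safety correction that is worth making because it is specific and nearly free.

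**What to change.** Reword the Coagulation row along these lines:

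> Any thromboembolic event: discontinue lenalidomide, and eltrombopag if it is being taken. For venous events of Grade 3 or higher, start anticoagulation. Restart neither drug until the event has resolved and proper prophylaxis is in place; lenalidomide may then restart at the investigator's discretion, with its dose level maintained.

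Do not make anticoagulation mandatory for arterial or lower-grade events. Neither text requires it, these patients are prone to thrombocytopenia, and Section 8.5 excludes anticoagulated patients from the bleeding analyses, so a wider mandate would also cost data on a secondary endpoint.

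The cost is one table row, taken through the amendment process in Section 15.2. No new procedure is added. The downside is that restart may be delayed when a clot resolves slowly, and the section's existing limits on unresolved toxicity and on the length of a lenalidomide hold could then take some patients off study. The paragraph already requires that wait.
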